## DATA AND RECORD KEEPING

**DATA COLLECTION:** Each subject will be assigned a unique study ID number once it has been determined they meet inclusion criteria. Subject outcome data will be collected using a secure web-based data collection form which will identify subjects only by their unique study ID and procedure date. Only the study investigators will have access to the list matching each subject ID to the patient's medical records, and only the PI and his immediate staff will enter follow-up data into the data collection form. The following data points will be collected for this study:

- pre-treatment clinical/ pathological description of disease
- TURBT date, location, and clinical description
- objective response, as confirmed upon surgical tumor resection,
- Neoadjuvant chemotherapy agent(s) and regimen used
- Pre and post-treatment CT scans (if available)

**RECORD KEEPING/CONFIDENTIALITY:** This information will be stored on password protected electronic systems managed by the study team. All hardcopies of study related documents will be kept in locked and secure files accessible only to the study team. The potential risk to subjects is the loss of confidentiality. To mitigate this risk, the data collection form contains no patient identifiers. As data are entered into the data collection form, the PI will create a master list that links the patient to her study identification number. This master list will be stored in a locked room in a locked cabinet with limited public access. The electronic files will be stored on a secure computer with password protection. To minimize the risk of lost confidentiality, only study investigators will have access to the list that links patient identifiers to the assigned study number. Once the patient is assigned a study identification number, that number will be used without additional patient identifiers whenever possible. All collected information will be stored electronically on an encrypted and password protected laptop.

**RISK ASSESSMENT:** This study involves only procedures and commercial therapeutic agents used in accordance with routine care practice and institutional guidelines. No increase in patient health risk is anticipated as a result of this study. There is a slight risk of loss of confidentiality of participant information. Every effort will be made to

keep participant information confidential. The PI is responsible for conducting continuous review of data and participant safety. At any time during the conduct of the trial, if it is the opinion of the investigators that the risk (or benefits) to the participants warrant early closure of the study, the study will be closed.

**CHANGES TO THE PROTOCOL:** Study procedures will not be changed without the mutual agreement of the Principal Investigator and co-investigators. If it is necessary for the study protocol to be amended, the amendment or a new version of the study protocol (amended protocol) will be generated by the Principal Investigator and must be approved by an IRB. Local requirements must be followed. If a protocol amendment requires a change to the Written Informed Consent Form, then the IRB must be notified. Approval of the revised Written Informed Consent Form by the IRB is required before the revised form is used. The Principal Investigator is responsible for the distribution of these documents to his IRB, and to the staff at his center. The distribution of these documents to the regulatory authority will be handled according to local practice.

## ETHICS:

The final study protocol, including the final version of the Written Informed Consent Form, must be approved by an IRB. The Principal Investigator is responsible for informing the IRB of any amendment to the protocol in accordance with local requirements. In addition, the IRB must approve any advertising used to recruit participants for the study. The protocol must be periodically re-approved by the IRB annually as local regulations may require. Progress reports and notifications of serious unexpected adverse events will be provided to the IRB according to local regulations and guidelines. The study will be performed in accordance with ethical principles originating from the Declaration of Helsinki, which are consistent with ICH/Good Clinical Practice, and applicable regulatory requirements.

**WRITTEN INFORMED CONSENT:** The investigator will ensure the participant is given full and adequate oral and written information about the nature, purpose, possible risks and benefits of the study. Participants must also be notified they are free to discontinue participation in the study at any time. The participant should be given the opportunity to ask questions and allowed time to consider the information provided. The participant's signed and dated informed consent must be obtained before utilizing any of the patient's health information or specimens for the study. The investigator must store the original, signed Written Informed Consent Form. A copy of the signed Written Informed Consent Form must be given to the participant. A copy of the Written Informed Consent Form is included in Appendix A.

**Appendix A – Written Informed Consent Form**

## Appendix B – Provider Workflow Checklist

### 1) Patient Screening

- a) Based on known tumor genetics, comorbidities, or other factors, is the patient highly unlikely to receive neoadjuvant chemotherapy? If “YES” then stop.
- b) Obtain patient informed consent document

### 2) Specimen Screening

- a) Is there at least 80mg of excess tumor specimen (approximately 3-4 loops) after preserving that which is necessary for routine pathology? If “YES” then proceed.

### 3) Specimen Preparation

- a) Open an Onco4D specimen collection kit (provided by Animated Dynamics) and apply the kit’s unique bar code identifier to patient paperwork using provided bar code labels. Place remaining bar code labels in patient file for use with additional paperwork in the future. This bar code will serve as the patient’s unique “Code” for purposes of identification throughout the study period, to reduce the risk of compromising protected health information.
- b) Place one copy of the patient informed consent signature in the collection kit (retaining one copy for the patient, and one for the practice).
- c) Collect two buccal swab samples using the matching bar coded swabs provided, replace in the zip top sleeve, and return to the collection kit.
- d) Dissect approximately 80mg of excess lesion:
  - i) Approximately 3-4 “loops” of tissue should yield sufficient specimen size
- e) Place fresh specimen(s) into bar coded vial in specimen collection kit ensuring that specimen is submerged in transport media, and seal vial.
- f) Place vial in zip top bag provided and seal bag.
- g) Place sealed bag in cooling kit along with buccal swabs.
- h) Place frozen ice pack in kit, close, and seal kit.
- i) Deliver Onco4D kit to Fedex courier as soon as possible (same day) for delivery to Animated Dynamics.).
- j) Record the association of the patient and the assigned Code for safekeeping.
- k) Forward pathology reports related to the TURBT procedure, as well as recommended chemotherapy regimen (if any) as soon as available.

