## PROJECT SUMMARY

In the US alone, millions of cancer patients every year receive chemotherapy with only a 20-60% probability of pathological response, while some experience adverse side effects that lower quality of life without necessarily prolonging it. Reliable identification of ineffective therapies can eliminate needless human suffering while increasing overall probability of positive response to treatment. Chemotherapy resistance profiling entails testing whether a patient exhibits strong resistance to a therapy prior to its final selection by the oncologist. However, there are no effective methods for quickly assessing patient chemotherapy resistance. Patient Derived Xenograft (PDX) models have replaced older Chemotherapy Sensitivity and Resistance Assays (CSRAs) to some degree, but both technologies suffer from long testing times, high cost, and/or low accuracy.

Motility Contrast Tomography (MCT) has recently emerged as a technology that measures the biodynamic response of intact tumor biopsies to applied therapeutics by using Doppler detection of infrared light scattered from intracellular motions inside living tissue. Several small scale animal, xenograft, and human studies have shown this phenotypic profiling technique to be highly accurate in prediction of response and resistance to chemotherapy. This project will be the first human trial of biodynamic phenotyping to predict chemotherapy response among bladder cancer patients. Specifically, the study cohort will include patients selected for neoadjuvant chemotherapy treatment, because this setting offers the opportunity for near-term outcome measurement at the time of post-chemo surgery. Pre-therapy fresh tumor specimens will be imaged using MCT, and the resulting bio-dynamic signatures will be compared to confirmed pathological response at the time of surgery. Observation of a high predictive value will provide the basis for expanded clinical trials and prompt commercialization of a biodynamic chemotherapy selection assay for bladder and other cancer patients.

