## STATISTICAL CONSIDERATIONS

**STUDY DESIGN:** This is a non-randomized, multi-arm, multi-center, feasibility study, designed to examine the feasibility of using MCT as a chemosensitivity assay among bladder cancer patients by comparing ex-vivo MCT patterns consistent with chemotherapy response and resistance to confirmed pathological response or resistance as measured by Response Evaluation Criteria in Solid Tumors (RECIST) v1.1 criteria.

**DEFINITION OF PRIMARY OUTCOME ENDPOINT:** Feasibility is defined as a high statistical correlation between MCT-predicted response, and surgically confirmed response to neoadjuvant chemotherapy.

**ANALYSIS PLAN FOR PRIMARY OBJECTIVE:** The study will be considered successful, if a majority of specimens yield interpretable MCT results, and if MCT signatures are identified which demonstrate a high statistical correlation to confirmed patient response.

**EXPLORATORY ANALYSIS:** Due to the inadequate samples size, no formal analysis is planned. Descriptive analysis of the correlation between MCT parameters and clinical outcome measures will be performed.

**DETERMINATION OF SAMPLE SIZE:** A target sample size of 500 patients was selected for initial enrollment using the investigators' previous research experience to approximate the appropriate number needed to demonstrate the feasibility of this technique. It is anticipated that only 20-30% of enrolled patients will yield specimens evaluable for response. It is estimated that it will take approximately 6-12 months to complete accrual.

**EVALUATION FOR RESPONSE:** Participants who provide a bladder tumor specimen, have received at least one cycle of chemotherapy, and have had their disease re-evaluated upon surgical resection will be considered evaluable for response.

**REPLACEMENTS:** Participants who withdraw from the study prior to having the TURBT procedure or fail to complete at least one evaluation for response will be replaced. No reported data will be included for participants who are replaced.

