### 4) Outcome Data

- a) As soon as practical after cystectomy, provide:

- i) neoadjuvant chemotherapy regimen given
- ii) pre and post-chemotherapy CT studies
- iii) pathology report from cystectomy specimen, including confirmed pathological response per RECIST v1.1 (if available)

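### Success depends on which specimens are called interpretable, but the protocol fixes neither that call nor the MCT values before response data are sent

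*Protocol*

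**What the plan says.** Statistical Considerations gives the success rule: "The study will be considered successful, if a majority of specimens yield interpretable MCT results, and if MCT signatures are identified which demonstrate a high" (the sentence ends by naming correlation with the response confirmed in patients). No definition of interpretable and no numerical meaning of high is given. The same section says "A target sample size of 500 patients was selected for initial enrollment" and "It is anticipated that only 20-30% of enrolled patients will yield specimens evaluable for response". Under exploratory analysis it adds "Due to the inadequate samples size, no formal analysis is planned".

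On the laboratory side, tissue is shipped for next-day delivery, imaged for a baseline of 2 to 4 hours, and then followed for at least 9 hours after drug is applied (Biopsy Sample Collection Parameters; Biopsy Sample Processing and Analysis). The section on measurement of effect by MCT lists the metrics and says that logistic regression combines them into one predictor. Neither part says who judges a specimen interpretable, by what criteria or when, nor when metric values become final. Research Design and Methods labels the study retrospective.

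On the clinical side, Appendix B has two steps. Under Specimen Preparation, item k reads "Forward pathology reports related to the TURBT procedure, as well as recommended chemotherapy regimen (if any) as soon as available". Under Outcome Data the instruction is "As soon as practical after cystectomy, provide", followed by the regimen given, the CT studies and the cystectomy pathology report with response.

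**The concern.** Both parts of the success rule work on a set of specimens that someone chooses. The first part counts those called interpretable; the second is a correlation among those kept. If a call can still be made or changed once response is known, specimens that disagree with the outcome can drop out more often than those that agree. No bad intent is needed: a poor-quality spectrum is easier to doubt when its prediction has failed. The correlation then rises while the majority condition is still met.

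This differs from fitting and judging a signature on the same data. Validating the signature within the retained specimens would not reveal a selection that had already taken place. The Project Summary makes a high predictive value the basis for expanded trials and commercial use, so a selected correlation would carry weight.

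**Working it through.** **The plan's own figure.** The target of 500 cannot be reproduced, because it rests on experience and no error rate, power or target correlation is given. Only the implied evaluable number follows: 500 × 0.20 = 100 and 500 × 0.30 = 150.

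**Assumptions, not in the protocol.** The assay has no value: calls are independent of outcome and half are positive. True concordance is then 50% at any response rate. A share *a* of concordant and *b* of discordant specimens is called uninterpretable.

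**Formulas.** Interpretable share = 1 − (a + b)/2. Apparent concordance = (1 − a)/(2 − a − b).

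- a = 20%, b = 20%: share 0.80; concordance 0.80/1.60 = 50%.
- a = 20%, b = 30%: share 0.75; concordance 0.80/1.50 = 53%.
- a = 20%, b = 40%: share 0.70; concordance 0.80/1.40 = 57%.
- a = 20%, b = 60%: share 0.60; concordance 0.80/1.20 = 67%.

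**Upper bound.** If a share k of all specimens is dropped and every one is discordant, concordance is 0.50/(1 − k): 55.6% at k = 10%, 71.4% at 30% and 98.0% at 49%. This bounds what the rule permits; it is not an expectation.

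**On the correlation scale.** The protocol speaks of correlation, so the same cases were simulated with 2,000 runs each, 100 and 150 patients, and response rates of 20%, 40% and 60%. That range comes from the Project Summary ("receive chemotherapy with only a 20-60% probability of pathological response"). The two-sided Fisher test at 0.05 is an illustration, since the protocol names no test. Ranges are over the six settings:

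- 20%/20%: mean phi about 0; p < 0.05 in 3.0–4.3% of runs.
- 20%/30%: phi 0.05–0.07; p < 0.05 in 5–10%.
- 20%/40%: phi 0.11–0.15; p < 0.05 in 12–30%.
- 20%/60%: phi 0.27–0.33; p < 0.05 in 47–85%, with the majority condition met in 97–99% of runs.

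**Denominator of the majority.** If it is all specimens, and each of 500 patients supplies one (an assumption), 251 must be interpretable and 500 − 251 = 249 need not be. That exceeds the 100 to 150 expected to be evaluable, so the rule would set no limit on exclusions among the patients who enter the correlation. The same holds whenever specimens number more than about twice the evaluable patients.

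**The case against.** The strongest reply is that this is an absence. Reader masking, interpretability criteria and data freezes often sit in an SAP or laboratory manual, and one may exist. That is why the bias can only be called possible. It does not dispose of the point: the success rule and the flow of reports are fixed in this protocol, and a freeze must operate specimen by specimen during conduct. An SAP written later could not restore it.

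Imaging does precede chemotherapy and surgery. That makes an early lock easy but does not impose one. Equally, the protocol does not say that calls are revised later; that is an inference from silence. Bar-coding and the restricted identity list in Data and Record Keeping protect identity, and do not say who may see outcomes. The recipient of the Appendix B reports is not named; the laboratory is only implied by the kit workflow.

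The calculation is also simplified. Discordance presupposes a prediction, and here the predictor is itself fitted, so the figures illustrate direction and scale only. A rule calling every patient a non-responder would reach 40–80% concordance at response rates of 60–20%, so concordance alone is not evidence of value. Any interpretability threshold below 100% allows exclusions; the majority rule does not create the problem.

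A reader might infer three stronger things, none supported:

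- That a worthless assay would appear 71% or 98% accurate. This needs every exclusion to be discordant.
- That item k unblinds the laboratory to response. It covers pre-treatment pathology and the recommended regimen, which do not reveal response.
- That response classification is contaminated by MCT results. No section returns those results to sites.

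**Conclusion.** The point holds as a gap in conduct that should be closed; it is not evidence of bias. The success rule uses an undefined interpretability call, response data are sent after cystectomy, and nothing in the protocol requires the call and the metric values to be fixed first.

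The size depends wholly on the assumed imbalance in exclusions. A mild one (20% against 30%) moves a no-value assay only from 50% to 53%. A marked one (20% against 60%) moves it to 67%, with a phi near 0.3 that would often reach nominal significance. Whether that would count as a high correlation cannot be said, because no value is set. With exclusions unrelated to outcome, concordance stays at 50%.

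**What to change.** In Biopsy Sample Processing and Analysis and in the section on measurement of effect by MCT, state that each specimen's interpretability call, made by written technical criteria, and its metric values are recorded and date-stamped after the imaging run and before that patient's response data are released to the laboratory. Log any later change and use it only in a sensitivity analysis. Report uninterpretable specimens by outcome.

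In Statistical Considerations, count the majority among response-evaluable specimens as well as among all specimens.

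Holding back the baseline reports of item k is secondary, and classifying response without knowledge of MCT is optional. The cost is a time-stamped freeze and a change log per specimen, with no extra patients or tissue and no change to care.

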### 4) Outcome Data

- a) As soon as practical after cystectomy, provide:

- i) neoadjuvant chemotherapy regimen given
- ii) pre and post-chemotherapy CT studies
- iii) pathology report from cystectomy specimen, including confirmed pathological response per RECIST v1.1 (if available)

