## CHEMOTHERAPY TREATMENT PLAN

**Administration and treatment schedule:** Registered participants will be treated per routine care guidelines and subject to treating physician discretion. Patients may be treated with an additional biologic agent if done within the confines of a separate clinical trial.

**General concomitant medication and support care guidelines:** Routine care guidelines should be followed at investigator discretion.

**Dose delays/modifications:** Dose adjustments for toxicity will be based on recommendations per the package insert and at the treating investigator's discretion.

**Duration of follow up:** Participants will be followed per routine care guidelines for progression.

**Criteria for removal:** Participants may withdraw from the study at any time at their own request, or they may be withdrawn at any time at the discretion of the investigator for safety, behavioral, or administrative reasons. Reasons for participant removal include: noncompliance with study procedures or follow-up procedures; participant withdrawal of consent and election to discontinue participation in the trial; any other reason which in the opinion of the investigator, would justify removing the participant from the study.

---

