## MEASUREMENT OF EFFECT - CHEMOTHERAPY

**Timing of response assessment:** In addition to a baseline scan (obtained within 35 days prior to registration), patients' response to chemotherapy will be evaluated immediately upon surgical tumor resection per routine care guidelines and according to institutional practice.

**Methods of response assessment:** Response and progression will be evaluated in this study using the new international criteria proposed by the revised RECIST guideline (version 1.1). Changes in the largest diameter (unidimensional measurement) of the tumor lesions are used in the RECIST criteria.

**Evaluable for objective response:** Only those patients who have measurable disease present at baseline, have received at least one cycle of neoadjuvant chemotherapy, and have had their disease re-evaluated upon surgical tumor resection will be considered evaluable for response. These patients will have their response classified

according to the definitions stated below. (Note: Patients who exhibit objective disease progression prior to the end of cycle 1 will also be considered evaluable.)

**Evaluable Non-Target Disease Response:** Patients who have lesions present at baseline that are evaluable but do not meet the definitions of measurable disease, have received at least one cycle of therapy, and have had their disease re-evaluated will be considered evaluable for non-target disease. The response assessment is based on the presence, absence, or unequivocal progression of the lesions.

**Measurable disease:** Measurable lesions are defined as bladder lesions that can be accurately measured in at least one dimension (longest diameter to be recorded) as  $\geq 2$  cm by cystoscopy or CT scan, MRI, or calipers by clinical exam. All tumor measurements must be recorded in millimeters (or decimal fractions of centimeters).

**Non-measurable disease:** All other lesions (or sites of disease), including small lesions (longest diameter  $< 2$  cm), are considered non-measurable disease for purposes of this study.

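### Patients who progress before the end of cycle 1 are declared evaluable, but those who never reach cystectomy have no defined route into the outcome data and can be replaced

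*Protocol*

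**What the plan says.** Five places in the protocol bear on this point.

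- **Measurement of Effect - Chemotherapy, evaluability for objective response.** The general rule covers patients with measurable baseline disease and at least one cycle of chemotherapy who "have had their disease re-evaluated upon surgical tumor resection will be considered evaluable for response". A note then adds: "Patients who exhibit objective disease progression prior to the end of cycle 1 will also be considered evaluable".
- **Chemotherapy Treatment Plan, duration of follow up.** "Participants will be followed per routine care guidelines for progression".
- **Statistical Considerations, evaluation for response and replacements.** Evaluability is stated again, for participants with a specimen and at least one cycle who "have had their disease re-evaluated upon surgical resection will be considered evaluable for response". The note on early progression is not repeated. Under the replacement rule, participants who withdraw before TURBT are replaced, as are those who "fail to complete at least one evaluation for response will be replaced. No reported data will be included for participants who are replaced".
- **The list of items to collect, under Data and Record Keeping.** The one response item is "objective response, as confirmed upon surgical tumor resection". The other items are the pre-treatment disease description, the TURBT details, the regimen used, and CT scans before and after treatment where these exist.
- **Appendix B, item 4, Outcome Data.** The instruction opens "As soon as practical after cystectomy, provide". Under it come the regimen given, the CT studies, and the "pathology report from cystectomy specimen, including confirmed pathological response per RECIST v1.1 (if available").

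**The concern.** The note on early progression is a deliberate exception: a patient whose disease grows during the first cycle has shown resistance, and the protocol wants that patient counted. Such a patient may never have a cystectomy. The rules and data items that should deliver the outcome all assume that surgery happens, so the exception exists in one section and is lost in the others.

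The study compares MCT patterns of sensitivity and resistance with what happened to the patient. Early progressors are unambiguous cases of resistance. If they drop out of the comparison while other patients stay, the sample is selected on outcome, and nothing recorded would show how many were lost or why. An analysis plan cannot repair this afterwards if progression and the reason for no surgery were never requested.

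**Working it through.** The protocol states no figure to reproduce. The sample size of 500 comes from the investigators' experience, without alpha, power or effect size. The check is a reading of the sections side by side, followed by an illustration of scale.

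**Following one patient through the text.** Take a patient who gives a specimen, starts neoadjuvant chemotherapy, progresses before the end of cycle 1 and has no cystectomy.

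1. Measurement of Effect - Chemotherapy: evaluable, by the note.
2. Statistical Considerations, evaluability: not evaluable, because resection is required and at least one cycle must have been received.
3. Statistical Considerations, replacements: can be replaced, with all data excluded, if no response evaluation is held to have been completed.
4. Data and Record Keeping: the response item is tied to resection. There is no item for progression, its date or basis, or for whether and why cystectomy was not done.
5. Appendix B, item 4: the trigger for sending outcome data never occurs.

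Steps 1 and 2 contradict each other. Steps 4 and 5 mean that, even if step 1 governs, the progression has no defined way of being reported.

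**Scale, for illustration only.**

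Inputs from the protocol:
- Target enrolment 500, and 20-30% expected to be evaluable (Statistical Considerations).
- Probability of pathological response 20-60% (Project Summary, for chemotherapy in cancer patients generally).

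Assumed, because the protocol gives no rate: a share e = 3% to 10% of otherwise evaluable patients progress in cycle 1 and have no cystectomy.

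- Expected evaluable patients: 500 × 0.20 = 100 to 500 × 0.30 = 150.
- Patients lost: 0.03 × 100 = 3 to 0.10 × 150 = 15.
- Share of non-responders lost, e / (1 − p), where p is the true response rate: lowest 0.03 / (1 − 0.20) = 3.75%; highest 0.10 / (1 − 0.60) = 25%. At the mid-point p = 40%: 0.03 / 0.60 = 5% to 0.10 / 0.60 = 16.7%.
- Response rate among those left, p / (1 − e): at p = 40%, 0.40 / 0.97 = 41.2% to 0.40 / 0.90 = 44.4%.

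The base is uncertain. The 100-150 may already exclude patients without surgery, since the definition in the same section requires resection. The number lost is then N × e / (1 − e): 100 × 0.03 / 0.97 = 3.1 to 150 × 0.10 / 0.90 = 16.7, which is close to the range above.

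**What this does not show.** The response rate is not the endpoint; the stated outcome is the correlation between MCT prediction and confirmed response. The effect on that correlation depends on what MCT would have shown in the lost patients. If it marked them as resistant, the study loses correct predictions; if as sensitive, it loses errors and the assay looks better than it is. The protocol gives no basis for choosing between the two.

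**The case against.** A reader might infer that early progressors cannot enter the data at all. The text does not go that far:

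- The outcome form is the web-based one in Data and Record Keeping, and that section sets no cystectomy trigger. Appendix B is a workflow checklist for providers.
- The CT item in the data list is not tied to surgery, so a scan showing progression could arrive that way.
- Progressive disease is a defined category under Response Criteria. An early progressor who still has surgery can be recorded as PD.
- Appendix B, item 3(k), has sites forward the TURBT pathology and the recommended regimen as soon as these exist. Patients meant to have chemotherapy can therefore be told apart from those who were not.
- Documented progression might be held to count as a completed response evaluation, in which case the replacement rule would not apply.

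These points narrow the problem to progressors without cystectomy, but do not remove it. The CT scans are collected only where available, and Appendix B requests them only after cystectomy. Item 3(k) conveys a recommendation, not an outcome. The reading of the replacement rule is possible but unstated, and it leaves the evaluability rule in Statistical Considerations as it is.

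A reader might also infer that complete responders who decline surgery are wrongly lost. They are not: the primary endpoint is response at surgery, both evaluability rules require resection, and the only exception is for early progression. These patients are non-evaluable by design. What is missing for them is only the reason for the loss.

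Finally, the loss rate used above is assumed and the figures concern the response rate. That criticism stands in full, and they show scale only.

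**Conclusion.** The point holds for patients who progress before the end of cycle 1 and never reach cystectomy. The protocol declares them evaluable in one section, omits them from the evaluability rule in another, permits their replacement with exclusion of their data, and gives no item or trigger by which their progression would be reported. This is an internal contradiction with a selective effect, since only non-responders are removed. It goes beyond detail that could be left to an analysis plan.

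Its size is unknown. On an assumed 3-10% of 100-150 evaluable patients it is 3-15 patients. The documents do not support a figure, or a direction, for bias in the correlation between MCT result and response. The conclusion rests on the text alone and does not depend on the assumed rate.

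**What to change.** - **Statistical Considerations.** Carry the early-progression exception into the evaluability rule, and state in the replacement rule that cycle-1 progressors are kept and classified as PD. Without this change, new data fields would not help, because the patient would still be non-evaluable there.
- **Appendix B, item 4.** Change the trigger to: after cystectomy, or once it is known that cystectomy will not take place.
- **Data and Record Keeping.** Add documented progression with its date and basis, and cystectomy done (yes or no) with the reason if not.
- **Reporting.** Show patients without cystectomy by reason. Those who decline surgery after an apparent complete response stay non-evaluable; only their reason is recorded.

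The cost is a few extra chart-abstraction fields per patient and one reworded trigger. No added scan or procedure is needed, and patient management does not change.
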